This study will provide a sequential evaluation of the composite hypothesis that (i) administration of hydrocortisone has efficacy benefit in that it reduces the risk of death or BPD at 36 weeks; and (ii) administration of hydrocortisone has an acceptable long-term safety profile with respect to death or NDI at 22-26 months. Specifically, the primary outcome for this study will include both a measure of efficacy (improvement in survival without BPD) and safety (survival without major NDI at 22 - 26 months corrected age). This composite hypothesis will be evaluated sequentially. First, point and interval estimates of the adjusted relative risk obtained from a robust Poisson regression model controlling for center and gestational age will be used to test the hypothesis that infants treated with hydrocortisone had a lower risk of death or BPD at 36 weeks than infants treated with placebo. If this test of efficacy indicates benefit of the hydrocortisone arm then the safety of the treatment will be evaluated descriptively through an assessment of the risk to benefit ratio of the hydrocortisone treatment. Specifically, this safety outcome will be considered a “success” if either (1) the point estimate of risk of death/NDI is lower on the hydrocortisone arm than on the control arm, or (2) there is an increase in risk on the hydrocortisone arm, but the lower limit of a one-sided 95% confidence interval for the ratio of increased benefit for BPD to increased risk for NDI is greater than 4. In other words, for every additional 4 infants surviving without BPD, no more than 1 additional infant would experience death/NDI.

(c) Power calculations and sample size:

Consistent with the approach for evaluating the composite hypothesis defined above, the sample size calculations were conducted in two stages. First, standard power

analysis software was used to assess the sample size required to demonstrate a difference in death or BPD at 36 weeks on the two treatment arms. Second, simulation analyses were used to assess the probability of success for the safety outcome based on either of the two criteria defined above. The empirical probability of success for the descriptive analyses used to evaluate the safety outcome is analogous to the power of a formal hypothesis test.

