(ii) Safety: In view of the previous data suggesting possible benefit from hydrocortisone treatment, we anticipate that hydrocortisone treatment will be associated with improved survival without moderate or severe neurodevelopmental impairment (defined “NDI”) in this population. However, we do not anticipate demonstrating a statistically significant benefit with this sample size. Instead, we postulate based on previous data that hydrocortisone will provide a 3% improvement in survival without NDI (19,20), and will consider this outcome successful if either (1) the risk of death/NDI is lower on the hydrocortisone arm than on the control arm, or (2) there is an increase in

death/NDI in the hydrocortisone arm, but the lower limit of a one-sided 95% confidence interval for the ratio of increased benefit for BPD to increased risk for NDI is greater than 4. In other words, for every additional 4 infants surviving without moderate or severe BPD, we would have 95% confidence that no more than 1 additional infant would experience death/NDI. For example, if we achieve the successful outcome of an increase of 10% in survival without moderate or severe BPD, we would hypothesize also achieving an increase of 3% in survival without NDI, but would only define the treatment as a success if there were no more than a 2.5% increase in death or NDI in the treatment arm. There are no existing standards for this balance of joint outcomes; however, this design will allow us to evaluate efficacy within a reasonable boundary of safety.

Conceptually, the power associated with the safety component of the composite test is the probability of achieving one of the two criteria defined above. To evaluate this probability, we simulated study outcomes for 10,000 studies with sample sizes in the range of 350 to 400 subjects per treatment arm. The prevalence of survival without BPD was assumed to be 25% to 35% on the control arm with the hydrocortisone arm providing an improvement of 10%. The probability of survival without NDI on the control arm was assumed to be 42% based on available NRN data with an assumed improvement of 1% to 3% on the hydrocortisone arm based on data available from the literature. The correlation between death or BPD at 36 weeks and death or NDI at 18 to 22 months was assumed to be in the range of 0.4 to 0.5 based on available data from the NRN GDB.

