The results indicate that if the improvement in the death or NDI outcome is only 1% on the hydrocortisone arm, then the probability of achieving a “success” on the safety outcome is 0.68 to 0.71 if success requires the lower limit of a 95% confidence interval on the risk benefit ratio to exceed 4, but 0.80 to 0.81 if we only require that the point estimate achieve 4. However, if the true benefit of the hydrocortisone treatment on death or NDI is at least 3% then the probability of achieving a “success” on the safety outcome is 0.83 to 0.86 if success requires the lower limit of a 95% confidence interval on the risk benefit ratio to exceed 4, and 0.90 to 0.93 if we only require that the point estimate achieve 4.

(d) Secondary outcomes and analysis: After analysis of unadjusted risk differences, other factors known to affect neurodevelopmental outcomes (such as gender, maternal education and dexamethasone exposure) will be entered into a multivariable analysis of outcome using the robust Poisson regression models described for the primary efficacy outcome for each of the binary secondary outcomes defined below. Secondary outcomes will include:

(i) Standard NRN measures of morbidity and growth as collected for the GDB at 36 weeks postmenstrual age and at 22 - 26 months corrected age. We will include ROP incidence and severity as a secondary outcome of specific interest, as there has been conflicting information regarding the relationship of dexamethasone to

ROP. We will also include a questionnaire to assess breathing outcomes at 22 - 26 months of age using forms developed for the SUPPORT study.

(ii) Successful extubation during the intervention period.

(iii) Use of open-label dexamethasone

(iii) Respiratory status at 40 weeks estimated gestational age. Assessment of respiratory outcomes at this age has been reported to more accurately predict long term respiratory outcomes (personal communication [name]). This assessment will not include a room air challenge, as repeating the physiologic testing would be burdensome and the 40 week status is not the primary study outcome.

(e) Concomitant medications will be recorded, in particular diuretics, bronchodilators, antibiotics, iNO, caffeine and Vitamin A.

(f) Safety monitoring:

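### Safety criterion (2) names no interval method, and its 95% confidence statement is not compatible with the success probabilities given for it

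*Combined protocol and SAP*

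**What the plan says.** METHODS/PROCEDURES (8)(b), on the primary outcome, sets a sequence: "If this test of efficacy indicates benefit of the hydrocortisone arm then the safety of the treatment will be evaluated descriptively". Safety succeeds on either of two criteria. Criterion (1) is met if "the point estimate of risk of death/NDI is lower on the hydrocortisone arm than on the control arm". Criterion (2) covers an increase in death/NDI and sets its test on a lower bound: "one-sided 95% confidence interval for the ratio of increased benefit for BPD to increased risk for NDI is greater than 4".

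Section (8)(c)(ii), Safety, repeats the rule and interprets it: for every 4 more infants surviving without BPD, "we would have 95% confidence that no more than 1 additional infant would experience death/NDI". Its example is that, with a 10% gain, the sponsor "would only define the treatment as a success if there were no more than a 2.5% increase in death or NDI". The section defines the safety power as the chance of meeting either criterion, with no conditioning on efficacy.

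For criterion (2) on the lower limit, the stated success probabilities are "0.68 to 0.71 if success requires the lower limit of a 95% confidence interval on the risk benefit ratio to exceed 4" at a 1% NDI improvement and "0.83 to 0.86 if success requires the lower limit of a 95% confidence interval on the risk benefit ratio to exceed 4" at 3%. If the point estimate decides instead, they are 0.80 to 0.81 and 0.90 to 0.93.

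No section names a method for the limit. The robust Poisson model in (8)(b) is for the relative risk of death or BPD, not for this ratio.

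**The concern.** B/R is a ratio of two estimated differences, and R is expected to lie near zero. Its lower limit depends heavily on whether the sampling error of R is carried. With that error ignored, criterion (2) can be met by a small observed rise in death/NDI. With it carried, criterion (2) is almost out of reach at this sample size. Two analysts following the same text could therefore reach different safety verdicts on the same data. The plan also attaches 95% confidence to the 4:1 balance, and whether that holds depends on the method left unstated.

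**Working it through.** **Inputs**, all from (8)(c)(ii) unless noted: 350 to 400 infants per arm, 1:1; control survival without BPD 25% to 35%, plus 10 points on hydrocortisone; control survival without NDI 42%, plus 1 or 3 points; correlation of the two outcomes 0.4 to 0.5. The budget's 15% deaths and 90% follow-up give 120 deaths + 612 followed = 732, or 366 per arm, inside this range.

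**Method.** Correlated binary pairs were drawn as four-cell multinomials in each arm, with 200,000 to 300,000 trials per scenario. B is the observed BPD gain and R the observed death/NDI increase. R of zero or less counts as success. For R > 0 the rules are:

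- estimate: B ≥ 4R
- R error-free: B - 1.645 SE(B) > 4R
- both errors: D = B - 4R > 1.645 SE(D), with Var(D) = Var(B) + 16 Var(R) - 8 Cov(B,R)

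**Step 1: the plan's own figures, unconditional.**

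| Rule | NDI +1% | NDI +3% |
|---|---|---|
| Plan, lower limit | 0.68-0.71 | 0.83-0.86 |
| R error-free | 0.69-0.71 | 0.83-0.86 |
| Both errors | 0.62-0.63 | 0.80-0.82 |
| Plan, estimate | 0.80-0.81 | 0.90-0.93 |
| Estimate rule | 0.79-0.82 | 0.90-0.92 |

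The estimate rule reproduces, so the simulation model is sound. The lower-limit figures reproduce on the same basis only with R error-free. Delta and log-delta limits that carry both errors gave the same result as the D contrast.

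**Step 2: why a both-error limit is almost unreachable.** Take 400 per arm, BPD 25% to 35%, NDI 42% to 45%, correlation 0.4:

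- Var(B) = (0.25×0.75 + 0.35×0.65)/400 = 0.0010375, so SE(B) = 0.032
- Var(R) = (0.42×0.58 + 0.45×0.55)/400 = 0.0012278, so SE(R) = 0.035
- Cov(B,R) = -0.4 × [√(0.1875×0.2436) + √(0.2275×0.2475)]/400 = -0.000451
- Var(D) = 0.0010375 + 0.019644 + 0.003608 = 0.02429, so SE(D) = 0.156

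Over the design scenarios SE(D) is about 0.155-0.160. With R just above zero, criterion (2) needs B > 1.645 × SE(D), about 26 points. It was met in none of the simulated trials, to the precision of the simulation. Success is then criterion (1) alone. A normal check at 400 per arm gives Φ(0.01/0.035) = 0.61 and Φ(0.03/0.035) = 0.80; counting exact ties as success adds about one point.

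**Step 3: confidence of each limit at a true ratio of 4** (B = 10 points, R = 2.5 points). The error-free limit allows a margin of 1.645 × 0.032 = 0.053 on D, about a third of SE(D) (0.053/0.156 = 0.34), where 1.645 is needed. By simulation it exceeds 4 with R > 0 in about 10-12% of all trials. The lower limit of D exceeds 0 in about 5.0-5.1%.

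**Step 4: a conditional reading.** Among trials with significant efficacy, a both-error limit gives 0.66-0.70 and 0.84-0.87, near the stated lower-limit figures. On that basis the estimate rule gives 0.86-0.89 and 0.95-0.96, which does not fit the 0.80-0.81 and 0.90-0.93 stated in the same sentences. It also departs from the unconditional definition in (8)(c)(ii).

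**The case against.** The probabilities come from a planning simulation. The analysis rule in (8)(b) and (8)(c)(ii) nowhere says that the death/NDI error will be ignored, and an analysis that carries both errors would have the stated confidence. This stands. A reader might infer that the sponsor did ignore that error, or that the trial cannot deliver its 95% confidence. The documents support neither: the method is inferred from a numerical match, an untried method might also match, and the shortfall arises only if that limit is used in the analysis. Nor do the lower-limit figures alone identify the method, as step 4 shows; it takes all four figures and the unconditional definition.

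The safety evaluation is called descriptive, and the plan says that no standard exists for such a balance. That softens the error-rate argument. Yet the plan gives the evaluation a success rule, likens its probability to power, and attaches 95% confidence.

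The practical difference is moderate: the two limits give different verdicts in about 7-9% of trials at +1% and 3-5% at +3%.

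A reader might also infer that the claim in (8)(c) of more than 80% probability of safety success is false. It is not shown to be: at the postulated 3% benefit the both-error figure is 0.80-0.82, so the claim is borderline. The 2.5% example is no error either; it is the boundary of the point ratio, 10/2.5 = 4. Equal death/NDI risk falls under neither criterion as worded, but ties occur in only about 2-3% of simulated trials, fewer if arm denominators differ or an adjusted model is used.

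**Conclusion.** The point holds and should be fixed. Criterion (2) lacks an interval method and, on the plan's unconditional definition, the stated lower-limit probabilities and the 95% confidence statement are not compatible. If the limit ignores the error in R, the probabilities hold but the error rate at a true ratio of 4 is about 10-12%, not 5%. If it carries both errors, the confidence holds, but criterion (2) adds practically nothing at the design effect and the success probability is about 6-9 points below the stated figure at +1% and 3-5 points below at +3%. This rests on the plan's own design inputs, unadjusted differences, equal arms and ties counted as success. The absence of a stated method is a matter of record; which method produced the figures is an inference.

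**What to change.** 1. In (8)(b) and (8)(c)(ii), define criterion (2) through D = B - 4R, with its standard error from the joint covariance of the two differences. Report D with its one-sided 95% lower limit.
2. State whether criterion (2) is judged on the lower limit of D or on the point estimate; this is the sponsor's choice. Use the 95% confidence sentence only where the lower limit of D exceeds 0. Describe success under criterion (1), or under a point-estimate rule, as a point-estimate result. In a clause, assign equal death/NDI risk to one criterion and label the 2.5% example as the point-ratio boundary.
3. Restate the success probabilities in (8)(c)(ii) for the chosen rule, saying whether they are conditional on efficacy. Unconditionally, at +1% and +3%, they are 0.62-0.63 and 0.80-0.82 for the both-error limit, or 0.79-0.82 and 0.90-0.92 for the point estimate.

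This costs some wording and a few lines of code, with no extra infants or data. The drawback is a plain trade: under the both-error limit the stated probability falls by about 6-9 points at +1% and 3-5 points at +3%; under the point-estimate rule it stays near the plan's second set of figures, but success carries no 95% confidence.

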As summarized in the subsections below, a sample size of 800 subjects will be adequate to provide the study with a power of 80% for the efficacy hypothesis and a probability of greater than 80% of a successful safety evaluation. With the population available (below), this sample size should allow completion of enrollment in less than 3 years, will give a clear answer regarding the efficacy of hydrocortisone for improving survival without moderate or severe BPD, and will allow a reasonable assessment of safety and potential benefit at 22 - 26 months corrected age.

(i) Efficacy:

Empirical studies of the effect of alternative analytic approaches for binary outcomes (e.g. tests of differences in proportions, logistic regression, Mantel-Haenszel tests, and Poisson regression models) indicate that unless the study has both substantial imbalance of sample sizes across strata and the substantial stratum-specific heterogeneity of treatment effect, power calculations for the various approaches can reasonably be approximated by standard tests for differences in proportions. Consequently, we used standard software to estimate sample sizes for a power of 0.80 under the assumption that the risk of death or BPD at 36 weeks on the control arm was in the range of 65% to 75% (or alternatively that the probability of survival without BPD was in the range of 25% to 35%). Considering a 10 percentage point difference in survival without BPD to be clinically significant, improving survival without BPD from approximately 25% in this population (historical NRN data) to 35% with a power of 0.80 would require a sample size of 658 infants. If the incidence of survival without BPD in the placebo group has improved over time to 35%, we can achieve a power of 0.80 to detect an increase to 45% with a sample size of 752. A sample size of 800 subjects will be adequate to assure that the study has a power of at least 80% to detect a 10 percentage point improvement in outcome regardless of the baseline incidence of survival without BPD, with a margin for a small loss in power if the treatment effect has modest heterogeneity across strata.

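### The worked safety example (10-point BPD gain, at most a 2.5-point rise in death/NDI) applies the ratio of 4 to point estimates, but criterion (2) applies it to a lower confidence limit

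*Combined protocol and SAP*

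**What the plan says.** Section (8)(b) of the combined protocol and SAP defines two routes to a successful safety outcome once efficacy has been shown. Criterion (1) is met if "the point estimate of risk of death/NDI is lower on the hydrocortisone arm than on the control arm". Criterion (2) covers an increase in risk on hydrocortisone and then sets this requirement: "lower limit of a one-sided 95% confidence interval for the ratio of increased benefit for BPD to increased risk for NDI is greater than 4".

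Section (8)(c)(ii) repeats both criteria and explains the second in words: for every 4 additional infants surviving without moderate or severe BPD, "we would have 95% confidence that no more than 1 additional infant would experience death/NDI". The next sentence is a worked example. It supposes a result, "if we achieve the successful outcome of an increase of 10% in survival without moderate or severe BPD", and says that the trial "would only define the treatment as a success if there were no more than a 2.5% increase in death or NDI". This is the only place where the tolerated rise is given in percentage points.

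The same section reports simulated probabilities of success for two separate rules. With the lower-limit rule they are 0.68 to 0.71 if hydrocortisone improves the death/NDI outcome by 1 point, and 0.83 to 0.86 if it improves it by 3 points. With the point-estimate rule they are 0.80 to 0.81 and 0.90 to 0.93.

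**The concern.** The example divides 10 by 4 to get 2.5. That is the boundary of the point-estimate rule, which the simulation paragraph treats as different from, and easier than, the rule adopted in (8)(b). The example therefore illustrates a rule that the plan did not adopt.

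This threshold decides the safety half of the primary outcome. Suppose the trial observes a 10-point BPD gain and a rise in death/NDI of, say, 2 points. A reader of the example would expect that result to count as acceptable, while criterion (2) rejects it. Differences of this size are plausible, because the plan itself works with effects of 1 to 3 points on this outcome. An ambiguity left in place until unblinding would have to be settled with the results in view.

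**Working it through.** **Inputs.** All come from sections (8)(c) and (8)(c)(ii): "sample sizes in the range of 350 to 400 subjects per treatment arm" in the simulation, and 400 per arm for the planned total of 800; control survival without BPD 25% to 35%, with a 10-point gain; control survival without NDI 42%, so control death/NDI 58%; correlation between the two adverse outcomes 0.4 to 0.5; one-sided 95%, z = 1.645.

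Write B for the observed gain in survival without BPD and N for the observed rise in death/NDI.

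**Step 1: reproduce the plan's figures.** Simulation of 200,000 trials per scenario over these ranges, with success if N < 0 or if the listed condition holds:

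| Condition | 1-point benefit | 3-point benefit |
|---|---|---|
| Point estimate: B > 4N | 0.79–0.81 | 0.90–0.92 |
| Only BPD error counted: B − 1.645·SE(B) > 4N | 0.68–0.71 | 0.83–0.86 |
| Both errors counted (Fieller; delta-method intervals agree) | 0.59–0.60 | 0.78–0.80 |
| Plan, point-estimate rule | 0.80–0.81 | 0.90–0.93 |
| Plan, lower-limit rule | 0.68–0.71 | 0.83–0.86 |

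The plan's lower-limit figures match the second row and not the third.

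A hand check of the second row, at 400 per arm, 25% baseline, correlation 0.4 and a 1-point benefit:
- Var(B) = 0.001038 and Var(N) = (0.58×0.42 + 0.57×0.43)/400 = 0.001222.
- A gain in survival without BPD goes with lower death/NDI, so the covariance of B and N is negative, with size 0.4×[√(0.1875×0.2436) + √(0.2275×0.2451)]/400 = 0.000450.
- Var(B − 4N) = 0.001038 + 16×0.001222 + 8×0.000450 = 0.0242, so SD = 0.1555.
- The mean of B − 4N is 0.10 + 0.04 = 0.14, and 1.645·SE(B) = 0.053. Success ≈ Φ((0.14 − 0.053)/0.1555) = 0.71.

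**Step 2: the example against the rule, without simulation.** At B = 10 and N = 2.5 the estimated ratio is exactly 4. A lower confidence limit lies below its estimate, so it is below 4 and criterion (2) is not met.

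**Step 3: tolerance when only the BPD error is counted.** SE(B) = √{[p(1−p) + (p+0.1)(0.9−p)]/n}. The lower limit is L = 0.10 − 1.645·SE(B), the largest rise that passes is L/4, and the ratio's lower limit at a 2.5-point rise is L/0.025.

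| n per arm | Survival without BPD | SE(B) | L (points) | Largest passing rise (points) | Lower limit of ratio at 2.5 |
|---|---|---|---|---|---|
| 400 | 25% to 35% | 0.0322 | 4.70 | 1.18 | 1.88 |
| 400 | 35% to 45% | 0.0345 | 4.33 | 1.08 | 1.73 |
| 350 | 25% to 35% | 0.0344 | 4.34 | 1.08 | 1.73 |
| 350 | 35% to 45% | 0.0368 | 3.94 | 0.98 | 1.58 |

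**Step 4: tolerance when both errors are counted.** The condition becomes B − 4N > 1.645·SE(B − 4N). At N = 0, 400 per arm, 25% baseline and correlation 0.4, Var(B − 4N) = 0.0241, so the right-hand side is 1.645×0.1553 = 0.255. Over the plan's ranges it runs from about 25 to 28 points. A 10-point gain falls short even with no rise at all. The break-even value of N is −3.9 to −4.6 points, so no increase passes and only criterion (1) could be met.

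**The case against.** The strongest reply is grammatical. The example says only if, which states a necessary condition. Any result that passes the lower-limit rule at a 10-point gain does have a rise below 2.5 points, so the sentence is literally true. A reader might infer that the plan declares a 10-point gain with a 2.5-point rise a success. The text does not go that far, and that part of the reply stands. The sentence is still offered as the worked example of the rule. As a bare necessary condition it would say nothing about rises between the rule's tolerance and 2.5 points, which is where a reader needs the guidance.

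A second reply is that 10 and 2.5 might be true effects to be ruled in or out with 95% confidence, in which case 4 is the correct boundary. The wording does not exclude this, but it speaks of achieving a 10% increase, which describes a result, and it mentions no limit.

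A third reply is that the criterion is stated in full in both (8)(b) and (8)(c)(ii), the safety evaluation is called descriptive, and none of the sample sizes 658, 752 and 800 was derived from the 2.5% figure. All of this is true, and it confines the defect to one sentence. That sentence nevertheless puts a number on a named success criterion for the primary outcome, and the plan does not say which text governs.

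**Conclusion.** The point holds as an inconsistency between the example and the rule. That an observed +10/+2.5 result fails criterion (2) is certain and needs no assumption about the interval.

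The size of the gap is conditional. If only the BPD error is counted, the tolerance at a 10-point gain is about 1.0 to 1.2 points. That this was the plan's construction is an inference from the match in Step 1, because the interval method is not stated. With the error in the death/NDI difference included, the tolerance is nil. The figures use unadjusted standard errors; covariate adjustment could move them somewhat, and the documents give no figure for that.

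A reader might infer that the printed tolerance is a fixed multiple, a little over twice, of the rule's tolerance. The documents do not support that as a general statement: 2.5/1.18 = 2.1 and 2.5/0.98 = 2.5 belong to the inferred construction only, and with both errors counted no multiple exists. Nor does it follow that 1.1 points is the correct replacement. That number ignores sampling error in the death/NDI difference and changes with baseline and sample size.

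**What to change.** Reconcile the example in (8)(c)(ii) with criterion (2), in one of two ways:

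- **If the lower-limit rule is kept:** state how the interval for the ratio is built, including whether it allows for error in both differences. Replace 2.5% with the tolerance that interval gives at the design values, labelled as illustrative and dependent on baseline and number per arm. If that tolerance is nil, say so.
- **If the point-estimate rule was intended:** say so in (8)(b) and (8)(c)(ii), and quote only the matching success probabilities (0.80 to 0.81 and 0.90 to 0.93).

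In either case, add that a point-estimate ratio of 4 does not by itself meet a lower-limit criterion. Which trade-off is acceptable is for the sponsor to decide, before unblinding.

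The cost is a small text edit with no new data. If the lower-limit rule is kept, the stated tolerance becomes less generous.

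### The confidence-limit success probabilities for the safety outcome (0.83–0.86 and 0.68–0.71) are higher than the stated rule delivers; a limit that carries both sampling errors gives 0.78–0.81 and 0.59–0.63

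*Combined protocol and SAP*

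**What the plan says.** Section (8)(b) evaluates safety after efficacy and gives two routes to success. The first is that "the point estimate of risk of death/NDI is lower on the hydrocortisone arm than on the control arm". The second applies when death/NDI is increased, with this requirement: "lower limit of a one-sided 95% confidence interval for the ratio of increased benefit for BPD to increased risk for NDI is greater than 4".

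Section (8)(c)(ii) then says that "the power associated with the safety component of the composite test is the probability of achieving one of the two criteria defined above". It reports a simulation of 10,000 trials and lists the inputs. For a true 1-point benefit on death/NDI the success probability is "0.68 to 0.71 if success requires the lower limit of a 95% confidence interval on the risk benefit ratio to exceed 4". For a 3-point benefit the corresponding statement reads: "on the safety outcome is 0.83 to 0.86 if success requires the lower limit of a 95% confidence interval on the risk benefit ratio" (again with 4 as the threshold). If only the point estimate of the ratio must reach 4, the figures are 0.80–0.81 and 0.90–0.93.

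The same section explains the ratio rule by saying that, for every 4 additional infants surviving without BPD, "we would have 95% confidence that no more than 1 additional infant would experience death/NDI". Its example is a 10% gain in survival without BPD, with success declared only "if there were no more than a 2.5% increase in death or NDI in the treatment arm".

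The opening of section (8)(c) summarises that 800 subjects give "a probability of greater than 80% of a successful safety evaluation". The documents do not say how the confidence limit of the ratio is computed, or how equal death/NDI counts are treated.

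**The concern.** The ratio has the death/NDI difference in its denominator. At 350 to 400 infants per arm that difference is estimated imprecisely, and the factor 4 magnifies its error. When the observed difference is a small increase, a proper lower limit for the ratio can hardly exceed 4. The second criterion should then add almost nothing, and the success probability should be close to the chance that observed death/NDI is lower. The stated figures sit clearly above that chance.

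The worked example points the same way. A 10-point gain with a 2.5-point increase has a point ratio of exactly 4, so its lower confidence limit must be below 4. The example fails the rule it is meant to illustrate.

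Section (8)(c) describes this probability as the counterpart of power, and it is half of the justification given for 800 infants. A reader would believe that the ratio criterion is a working safeguard that contributes successes, and that the rule has a comfortable margin over 80%.

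**Working it through.** **Inputs, all from section (8)(c)(ii) except the 1:1 allocation in section (4)(b):** n = 350 or 400 per arm; survival without BPD 25% or 35% on control, plus 10 points on hydrocortisone; survival without NDI 42% on control, plus 1 or 3 points; correlation of the two outcomes 0.4 or 0.5. This makes 16 settings, simulated as correlated binary pairs with 200,000 trials each (3,200,000 in all).

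Let B be the observed gain in survival without BPD and H the observed increase in death/NDI.

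**Step 1. Reproduce the plan's point-estimate figures.** Success is H ≤ 0, or H > 0 with B/H ≥ 4. The result is about 0.80–0.82 at 1 point and 0.90–0.92 at 3 points, against the stated 0.80–0.81 and 0.90–0.93. The set-up is therefore the plan's own.

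**Step 2. Apply the confidence-limit rule with both errors.** For H > 0, a lower limit of B/H above 4 is equivalent to a lower limit of B − 4H above 0:

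B − 4H > 1.645 × SE(B − 4H), where SE² = Var(B) + 16 Var(H) − 8 Cov(B, H).

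The covariance is negative, because survival without BPD and survival without NDI go together, so the last term adds to the variance. At a 3-point benefit, the two extreme settings are:
- n = 400, BPD-free survival 25%, correlation 0.4: Var(B) = (0.1875 + 0.2275)/400 = 0.00104; Var(H) = (0.2436 + 0.2475)/400 = 0.00123; Cov = −0.00045. SE² = 0.00104 + 0.01964 + 0.00361 = 0.0243, so SE = 0.156.
- n = 350, BPD-free survival 35%, correlation 0.5: Var(B) = (0.2275 + 0.2475)/350 = 0.00136; Var(H) = 0.4911/350 = 0.00140; Cov = −0.00069. SE² = 0.00136 + 0.02245 + 0.00552 = 0.0293, so SE = 0.171.

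For an increase of one infant, H = 1/n, the required gain is B > 1.645 × SE + 4/n. This is 0.256 + 0.010 = 0.266 in the first setting and 0.282 + 0.011 = 0.293 in the second. A gain of about 27 to 29 points is needed, against the assumed 10. In the simulation, criterion (2) was met in 0 of 3,200,000 trials; the largest z seen in any run was 1.51, against 1.645. Delta and log-delta limits gave the same success probabilities to three decimals. A percentile bootstrap also added nothing (4,000 trials at each of 5 settings).

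**Step 3. Compute what remains exactly.** Success is now the chance that the hydrocortisone arm has fewer death/NDI cases, from two independent binomials with survival without NDI of 0.42 and 0.43 or 0.45.

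| n per arm | Benefit | Ties fail | Ties succeed | Stated |
|---|---|---|---|---|
| 350 | 3 points | 0.777 | 0.799 | 0.83–0.86 |
| 400 | 3 points | 0.794 | 0.814 | 0.83–0.86 |
| 350 | 1 point | 0.591 | 0.620 | 0.68–0.71 |
| 400 | 1 point | 0.599 | 0.626 | 0.68–0.71 |

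Matching low end to low end and high end to high end:
- 3 points: 0.83 − 0.799 = 0.03 up to 0.86 − 0.794 = 0.07.
- 1 point: 0.68 − 0.620 = 0.06 up to 0.71 − 0.599 = 0.11.

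The Monte Carlo standard error of 10,000 runs is √(0.8 × 0.2/10,000) = 0.004, and 0.005 at 0.62. Simulation noise does not explain the gap.

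**Step 4. Find what does return the stated figures.** Treat H as known without error, so the condition is (B − 1.645 × SE(B))/H > 4, and count ties as success. This gives 0.69–0.72 and 0.83–0.86, matching the plan. That this was the method used is an inference.

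**Step 5. Test the example.** With B = 0.10 and H = 0.025, B − 4H = 0, and its lower limit is −1.645 × (0.156 to 0.171), or about −0.26 to −0.28. Even the limit of step 4 does not allow it. SE(B) is √0.00104 = 0.032 to √0.00136 = 0.037, so the lower limit of B is 0.10 − 1.645 × SE(B) = 0.047 to 0.039. Divided by 4, that permits an increase of 1.0 to 1.2 points, not 2.5.

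**The case against.** The strongest objection is that the interval method is unstated, and that one simple limit (error of the BPD gain only, ties as success) approximately recovers all four published ranges. On that view the simulation is right for the limit used, and the fault is one of specification. It stands that the method is unspecified and that the source of the figures is inferred. But a limit that ignores the error of the death/NDI difference is not a 95% limit for the ratio, and cannot support the confidence statement made in the same section.

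A second objection is that section (8)(b) judges safety only after efficacy is shown. Among trials with significant efficacy, the both-errors limit with ties as success gives 0.67–0.70 and 0.84–0.87, close to the stated confidence-limit figures. This is a fair alternative reading of those two ranges. However, the same conditioning moves the point-estimate rule to 0.87–0.89 and 0.95–0.96, against the stated 0.80–0.81 and 0.90–0.93, and section (8)(c)(ii) states no conditioning. Of the readings tried, none with a both-errors limit returns both sets.

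Third, the stakes are limited, and this largely stands. Safety is assessed descriptively, and 800 is driven by the efficacy requirements of 658 and 752. The lower probability at a 1-point benefit is openly reported. At 400 per arm and 3 points with ties as success, the summary claim still holds (0.814).

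**Conclusion.** The concern holds. With a limit that carries both sampling errors, the success probability is 0.78–0.81 at a 3-point benefit and 0.59–0.63 at 1 point, the spread coming from sample size and the tie rule. Both stated ranges lie wholly above these. At the planned 800 infants and a 3-point benefit, the claim of more than 80% is borderline: 0.794 under the literal wording of a lower estimate, 0.814 if ties count. At a 1-point benefit it fails even on the plan's own figures.

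The larger consequence is interpretive. Criterion (2) adds practically no successes at this size, so the operating rule is simply that observed death/NDI is lower. The conclusion rests on the plan's stated inputs and on unconditional probabilities. It does not depend on the choice among the Fieller, delta, log-delta and bootstrap limits tried. The efficacy sample size is unaffected.

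**What to change.** 1. In sections (8)(b) and (8)(c)(ii), state how the limit is computed (for example a Fieller limit, or the lower limit of BPD gain minus 4 times the death/NDI increase, with their covariance) and whether equal death/NDI counts as success.
2. Re-run the simulation under that definition and say whether the probability is conditional on the efficacy test. With a both-errors limit and no conditioning, expect about 0.78–0.79 (ties fail) or 0.80–0.81 (ties succeed) in place of 0.83–0.86, and 0.59–0.60 or 0.62–0.63 in place of 0.68–0.71. If a limit using only the BPD error was intended, say so and withdraw the 95% confidence statement.
3. In the opening of section (8)(c), replace the unqualified claim with about 0.80 at 800 infants for a 3-point benefit and about 0.6 for 1 point.
4. Note that the ratio criterion adds practically no successes at this sample size.
5. Label the 10%/2.5% example as a point-estimate illustration, or reconcile it with the confidence-limit rule.

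The cost is protocol wording and a short re-run. The figures become less favourable; no extra infants are needed.
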